- 1.2. A viral etiology of IPF was first suspected more than half a century ago, but identification of an important role for viruses in IPF pathogenesis has been challenging(2). In 2003, our group used a PCR strategy for identification of all known herpesviruses in lung tissue samples and found that 97% of lungs from IPF patients contained herpesvirus DNA(3). Importantly, viral proteins were expressed in AECs lining areas of fibrosis in IPF lungs, but were not detected in AECs in normal lungs. To investigate the prevalence of herpesvirus antigens in AECs of IPF patients, we performed IHC on lung sections from 34 individuals with IPF and 10 normal control lungs for cytomegalovirus (CMV) and Epstein-Barr virus (EBV), the most common herpesviruses in the lungs of IPF patients. We identified expression of EBV and/or CMV proteins, which is indicative of chronic infection or viral reactivation, in AECs from 29/34 patients (85%) with IPF and 0/10 normals. We also showed that expression of herpesvirus antigens in IPF co-localizes with markers of endoplasmic reticulum (ER) stress, which is common in IPF and may contribute to AEC dysfunction and apoptosis(4). Recently, we identified DNA for CMV and EBV in cell-free fluid obtained by bronchoalveolar lavage (BAL) from IPF patients and controls. Using standard PCR to identify DNA for EBV and CMV in concentrated DNA from cell-free BAL, we found that 21/28 IPF subjects were positive for CMV and 6/28 were positive for EBV DNA (23/28 were positive for at least one herpesvirus). Taken together, these data suggest that herpesvirus infection of alveolar epithelial cells is common in IPF and could contribute to fibrosis.
- 1.3. In addition to the considerable evidence implicating herpesviruses in human IPF, a number of animal model studies have also indicated that herpesviruses could play a pathogenic role in lung fibrosis(5, 6). Given this combination of evidence for a role for herpesviruses in IPF and the fact that oral treatments for herpesviruses are already available with a proven track record, we propose this timely study evaluating the effectiveness of anti-herpesvirus treatment in IPF.

2. Hypothesis: Addition of valganciclovir to standard IPF treatment has an acceptable safety and tolerability profile.

3. Specific Aims

3.1 To determine the safety and tolerability of oral valganciclovir as add-on therapy in patients with IPF tolerating standard treatment with pirfenidone. 30 individuals with a diagnosis of IPF and positive serology for EBV or CMV will be enrolled in this study at Vanderbilt University Medical Center and randomized to receive either valganciclovir or placebo in a 2:1 ratio for 12 weeks. The primary endpoint will be rate of discontinuation of study drug due to adverse events in subjects randomized to valganciclovir compared to placebo. In addition, we will compare type, frequency and duration of adverse events (AE) and serious adverse events (SAE) between valganciclovir and placebo subjects.

3.2 To investigate the effect of anti-herpesvirus treatment on changes in viral load and immune responses against herpesvirus. A subset of study subjects will undergo bronchoscopy with BAL at the time of study entry and at 12 weeks for measurement of: 1) immune response to herpesviruses in lung lymphocytes and 2) herpesvirus DNA in cell-free BAL fluid. Additional studies to investigate changes in the immune response in peripheral blood lymphocytes to herpesviruses will include: 1) analyzing PD-1 expression by T lymphocytes and 2) quantifying CD8+ T cell immune responses to herpesvirus antigens at study entry and after 12 weeks of therapy. These parameters will be reassessed at 6 months and 1 year after study entry

to determine whether changes in anti-herpesvirus immune responses persist or revert to pre-treatment levels, thus shedding light on the duration of therapy needed to potentially alter disease progression.

4. Endpoints

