4.1. Primary Endpoint

4.1.1. The primary outcome will be safety and tolerability will be determined by type, frequency and duration of adverse events (AE) and serious adverse events (SAE) in subjects receiving valganciclovir versus placebo.

4.2. **Secondary Endpoints:** We will evaluate for trends in other clinical endpoints, as well as viral and immune endpoints over time in the valganciclovir group compared to the placebo group.

4.2.1. We will determine the change in pulmonary function tests including forced vital capacity (FVC) and diffusing capacity for carbon monoxide (DLCO) in the valganciclovir treated group compared to placebo during active treatment and post-treatment follow-up. PFTs will be measured at baseline, 3 months (12 weeks), 6, 9 and 12 months after randomization to determine the FVC slope (change in FVC over time) and change in diffusion capacity (DLCO).

4.2.2. We will determine the effect of valganciclovir therapy on viral load in cell-free BAL fluid.

4.2.2.1. We will evaluate the change from baseline in daytime oxygen requirements. Oxygen requirements will be measured at study visits baseline, 3, 6, 9, 12 months. At each study visit, while at rest, the subject will be placed on the amount of supplemental O₂ required at the enrollment visit. After 5 minutes, the SpO₂ on this supplemental flow rate will then be recorded and evaluated in comparison to baseline. In addition, the patient will have his/her supplemental oxygen requirement determined to maintain oxygen saturation $\geq 88\%$ at rest. The change in liters per minute flow rate in oxygen compared to baseline will be recorded.

4.2.3. Exercise capacity will be determined on the basis of the 6 minute walk test (6MWT). The principal exercise capacity measurement will be the change in distance until SpO₂ reaches 80% compared to baseline. 6 MWT will be measured at study visits baseline, 3, 6, 9, 12 months. The 6MWT will be performed using a standardized protocol while the subject is breathing room air (i.e. without supplemental oxygen).

4.2.4. Additional secondary endpoints will analyze the immune response to herpesviruses by analyzing PD-1 expression by T lymphocytes and quantifying CMV- and EBV-antigen specific CD8⁺ T cell immune responses.

5. Background and Significance

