Randomization will be to pirfenidone plus placebo or pirfenidone plus valganciclovir. We prefer to have all subjects on pirfenidone as the standard of care for this study since the majority of patients elect to be treated with pirfenidone in our clinic. In addition, we anticipate valganciclovir will be better tolerated in combination with pirfenidone. We propose to enroll and randomize all eligible subjects with evidence of current or past EBV or CMV infection as determined by serologic testing for anti-EBV and CMV antibodies (total n=30) to treatment with pirfenidone plus valganciclovir (20 patients) or pirfenidone plus placebo (10 patients) for 12 weeks (**Fig. 1**). In order to maximize exposure to active treatment and assess for safety and tolerability, randomization will be 2:1 valganciclovir vs. placebo. The primary outcome will be safety and tolerability will be determined by type, frequency and duration of AE and SAEs. All study subjects will be offered bronchoscopy with BAL at study initiation and upon completion of treatment (12 weeks). Subjects will then be followed up at routine clinic visits at 6, 9 and 12 months for data collection.

[figure not shown]

Figure 1. Study flow chart.

6.2 **Rationale for Blinding and Placebo:**

6.1.1. A RCT is necessary given the clinical heterogeneity of IPF, and the inability to have two similar arms without randomization. A placebo arm will minimize bias since GI upset is a side effect of valganciclovir and standard treatment, pirfenidone. All subjects will be provided standard of care treatment to be applied equally across study groups as much as feasible and blinding will help avoid bias in the care provided.

6.1.2. Blinding is necessary to have optimal scientific validity, to make objective assessments of treatment effects, and to minimize dropout rates across study arms. In this study, there is particular concern that without blinding, subjects may opt to obtain off-label anti-viral therapy from non-study physicians if they become aware of the presence of herpesviruses in their lungs.

7. **Study population:** The study population will consist of male and female patients diagnosed with IPF, ages 21 and above, who are followed in the outpatient clinic setting.

7.1. **Inclusion criteria** will be:

- 7.1.1. age ≥ 21 and ≤ 80 years
- 7.1.2. ability to provided informed consent
- 7.1.3. diagnosis of probable or definite IPF according to ATS criteria(11)

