13.2. Sample Size and Randomization

- 13.2.1. Power analysis: This pilot study is designed to determine tolerability and safety of valganciclovir as add-on therapy to pirfenidone. Pirfenidone is reported to be discontinued in 13% of subjects due to adverse events, almost all of which occur within the first 4 weeks of treatment (based on AE profiles from the ASCEND study). Therefore, we do not expect any

placebo treated subjects to withdraw from this study. Using a 2:1 randomization (valganciclovir:placebo) and enrolling 30 subjects will allow us to detect an increased withdrawal rate in the valganciclovir group in the range of 25% (75% power with a one-sided $\alpha=0.1$). Subjects who require dose reduction, or temporary discontinuation but are able to resume treatment will be considered non-withdrawals.

13.2.2. **Randomization:** The randomization scheme will be a ratio of 2:1 for drug versus placebo. Once a participant has signed the consent form and completed the enrollment visit (and baseline bronchoscopy in subjects who participate in the bronchoscopy substudy), the participant will be randomized. Study medication will be distributed by the VUMC investigational pharmacy according to the randomization scheme.

13.3. **Statistical analysis:** For the primary endpoint, the rate-of-discontinuation of study drug due to adverse events will be compared between valganciclovir and placebo subjects by Chi-square. **Secondary analysis:** Frequencies of specific adverse event profiles will be compared between groups by Chi-square. This study is not powered to detect clinically significant changes in pulmonary function or perform multivariate analyses. Exploratory analyses for physiologic and biochemical endpoints will be performed using standard nonparametric statistics or paired tests when appropriate. The rate of change in FVC (cc/year) will be compared between valganciclovir therapy group (treatment group) compared to the standard of care (placebo) group. For other physiologic measurements (6MWD, oxygenation), similar analyses will be performed. For exploratory biomarker studies, paired analyses (Baseline vs. 12 weeks) will be performed comparing subjects randomized to valganciclovir or placebo. All analyses will be performed using STATA 11.0 (StataCorp, College Station, TX) and the programming language R (50).

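### The hypothesis is acceptable tolerability, but the primary analysis is a test of difference with no interval or limit, so a non-significant result in 20 v 10 subjects cannot support it.

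*Combined protocol and SAP*

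**What the plan says.** Section 2 gives the hypothesis as "Addition of valganciclovir to standard IPF treatment has an acceptable safety and tolerability profile". Aim 1 (section 3.1) makes it operational: "The primary endpoint will be rate of discontinuation of study drug due to adverse events in subjects randomized to valganciclovir compared to placebo". Section 4.1.1 describes the primary outcome differently, as the type, frequency and duration of adverse and serious adverse events. It sets no limit either.

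For the analysis, 13.3 says that "the rate-of-discontinuation of study drug due to adverse events will be compared between valganciclovir and placebo subjects by Chi-square". The secondary safety analysis is of the same kind: "Frequencies of specific adverse event profiles will be compared between groups by Chi-square". Section 13.3 names no alpha, sidedness, continuity correction or confidence interval.

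Section 6.1 fixes the size: "pirfenidone plus valganciclovir (20 patients) or pirfenidone plus placebo (10 patients) for 12 weeks". Section 13.2.1 says of withdrawals in placebo subjects that "we do not expect any". It gives 75% power at one-sided alpha 0.1 for an increased withdrawal rate of about 25%. Section 14 terminates the study if valganciclovir has 5 more adverse-event withdrawals than placebo at a look after 10 or 20 subjects are enrolled. No section says what final result would count as acceptable.

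**The concern.** A chi-square test of no difference can give evidence that valganciclovir is worse tolerated than placebo. It cannot give evidence that it is tolerated well enough, because a large p-value may only reflect 20 v 10 subjects. The stated hypothesis is therefore not linked to any analysis that could confirm it.

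At stake is the main message of the pilot. A report of no significant difference in discontinuation could be carried into a larger trial as evidence of tolerability, although the data might be compatible with nearly half of valganciclovir patients stopping. The quantity that addresses the hypothesis, an upper bound on the discontinuation rate, is not among the planned outputs.

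**Working it through.** **Inputs.** n = 20 and 10 (6.1). True rates 25% v 0%, one-sided alpha 0.10, stated power 75% (13.2.1). Test: chi-square (13.3).

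**1. The plan's own power.** Normal approximation, with pooled variance under the null and unpooled under the alternative:
- Pooled rate = (20 × 0.25 + 10 × 0)/30 = 0.1667.
- SE under the null = √(0.1667 × 0.8333 × (1/20 + 1/10)) = 0.1443.
- SE under the alternative = √(0.25 × 0.75/20) = 0.0968.
- Power = Φ((0.25 − 1.2816 × 0.1443)/0.0968) = Φ(0.67) = 74.9%.

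The stated 75% reproduces, so the point is not an arithmetic error.

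**2. Which results would be non-significant.** The uncorrected statistic is z = (x/20 − y/10)/√(p(1−p) × 0.15), with p = (x + y)/30, x valganciclovir events and y placebo events. Upper bounds are exact (Clopper-Pearson), one-sided 90%: the 0.90 quantile of Beta(x + 1, 20 − x).

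| Reading of 13.3 | Placebo events | Largest non-significant x | 90% upper bound |
|---|---|---|---|
| Uncorrected chi-square, one-sided 0.10 | 0/10 | 2/20 (z = 1.035, p = 0.150) | 24.5% |
| Uncorrected chi-square, one-sided 0.10 | 1/10 | 6/20 (z = 1.221, p = 0.111) | 46.7% |
| Fisher, one-sided 0.10 | 0/10 | 5/20 (p = 0.109) | 41.5% |
| Uncorrected chi-square, two-sided 0.05 | 0/10 | 6/20 (z = 1.936, p = 0.053) | 46.7% |

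In the first row 3/20 is significant (z = 1.291, p = 0.098). In the second row 7/20 is significant (z = 1.460, p = 0.072).

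**3. Chance of missing a true 25% v 0%.** With no placebo events possible, this is the binomial probability, n = 20 and rate 0.25, of staying at or below the cut-off:
- uncorrected chi-square, one-sided 0.10: P(X ≤ 2) = 9.1%
- Fisher, one-sided 0.10: P(X ≤ 5) = 61.7%
- uncorrected chi-square, two-sided 0.05: P(X ≤ 6) = 78.6%
- the plan's own normal approximation: 25%

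**4. How secure the zero in placebo is.** The favourable row needs 0/10. If the true placebo rate were 5% (an assumption, not in the plan), at least one event would occur in 1 − 0.95^10 = 40% of trials. The cut-off would then be at least 6/20.

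**5. What the interim rule adds.** Assume splits of 7:3 and 13:7 at the two looks, complete follow-up and true rates of 25% v 0%. The chance of 5 excess withdrawals is then 1.3% at the first look and 20.6% at the second. The rule rarely acts at that rate, and it sets no standard for the final result.

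**6. What an upper bound would deliver at the present size.** If 25% is used as a reference, the 90% bound lies below it when x ≤ 2. That happens in 92% of trials at a true rate of 5%, 68% at 10%, 40% at 15% and 9% at 25%.

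**The case against.** The best defence is that the plan names chi-square, and that the only alpha it states anywhere is one-sided 0.1. On that reading, with no placebo events as 13.2.1 expects, a non-significant result means 2/20 or fewer. That is the same cut-off, with the same 9% error at a true 25%, as requiring the 90% bound to fall below 25%. This stands, and it limits the seriousness of the point. It does not remove it: 13.3 does not commit to that reading, and one placebo event moves the cut-off from 2/20 to 6/20.

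Some stronger readings are tempting but not supported by the documents:
- A reader might infer that discontinuation is the only safety comparison. It is not: 13.3 also compares adverse event frequencies, and 11.1.2 and 11.1.3 set out laboratory, examination and graded adverse event review. However, the frequency comparisons are also tests of difference without a limit.
- A reader might infer that the trial will declare acceptability on a non-significant p-value. No section says so. The defect is that no rule of interpretation is given.
- A reader might take the 62% or 79% miss rate as that of the planned test. These belong to Fisher's test and to a two-sided 0.05 level, neither of which the plan names. They show the cost of leaving the choice open.
- A reader might take 25% as an acceptability ceiling. In 13.2.1 it is a detectable increase over placebo, not a limit on the valganciclovir rate. A rule built on it is also fragile: 2/20 gives 24.5%, but 2/19 gives 25.7%.

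It is also fair to say that this is a 30-subject pilot and that exact bounds can be worked out from the reported counts. But tolerability is the pilot's stated purpose, and estimation suits this size better than a test does.

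**Conclusion.** The point holds in a limited form. The hypothesis is one of acceptability, while every planned between-arm safety test is a test of difference. No interval, bound or limit ties the final result to the hypothesis, and the section 14 rule governs interim stopping only. A non-significant primary test therefore cannot support section 2.

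The consequence ranges from slight to large. It is slight with the uncorrected test at one-sided 0.10 and 0/10 on placebo. It is large with one placebo event, or with a more conservative test or level: observed discontinuation of 25% to 30% would then be non-significant, with upper bounds of 41.5% to 46.7%. These figures assume all 20 and 10 subjects are evaluable. The miss rates also assume true rates of 25% v 0%. The change should be made, but the point does not undermine the design.

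**What to change.** In 13.3:
1. Report as the primary result the proportion of valganciclovir subjects discontinuing for adverse events, with an exact one-sided 90% upper bound (matching the alpha of 0.1 in 13.2.1). Report with it the valganciclovir-minus-placebo risk difference with an exact confidence interval.
2. Base the tolerability conclusion on these intervals, and state that a non-significant p-value is not evidence of acceptability.
3. Keep the between-arm test as supportive, and write the one-sided 0.10 of 13.2.1 into 13.3.
4. If a numerical limit is wanted, the sponsor should choose and justify it before unblinding and refer to it in section 2. The 25% can serve as a reference, not as a limit the plan already contains.

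The cost is wording only: no patients, visits or data. The conclusion may be somewhat harder to reach. With 25% as the reference, the chance of 2/20 or fewer falls from 92% at a true 5% to 68% at 10% and 40% at 15%.

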4.1. Primary Endpoint

4.1.1. The primary outcome will be safety and tolerability will be determined by type, frequency and duration of adverse events (AE) and serious adverse events (SAE) in subjects receiving valganciclovir versus placebo.

4.2. **Secondary Endpoints:** We will evaluate for trends in other clinical endpoints, as well as viral and immune endpoints over time in the valganciclovir group compared to the placebo group.

4.2.1. We will determine the change in pulmonary function tests including forced vital capacity (FVC) and diffusing capacity for carbon monoxide (DLCO) in the valganciclovir treated group compared to placebo during active treatment and post-treatment follow-up. PFTs will be measured at baseline, 3 months (12 weeks), 6, 9 and 12 months after randomization to determine the FVC slope (change in FVC over time) and change in diffusion capacity (DLCO).

4.2.2. We will determine the effect of valganciclovir therapy on viral load in cell-free BAL fluid.

4.2.2.1. We will evaluate the change from baseline in daytime oxygen requirements. Oxygen requirements will be measured at study visits baseline, 3, 6, 9, 12 months. At each study visit, while at rest, the subject will be placed on the amount of supplemental O₂ required at the enrollment visit. After 5 minutes, the SpO₂ on this supplemental flow rate will then be recorded and evaluated in comparison to baseline. In addition, the patient will have his/her supplemental oxygen requirement determined to maintain oxygen saturation $\geq 88\%$ at rest. The change in liters per minute flow rate in oxygen compared to baseline will be recorded.

4.2.3. Exercise capacity will be determined on the basis of the 6 minute walk test (6MWT). The principal exercise capacity measurement will be the change in distance until SpO₂ reaches 80% compared to baseline. 6 MWT will be measured at study visits baseline, 3, 6, 9, 12 months. The 6MWT will be performed using a standardized protocol while the subject is breathing room air (i.e. without supplemental oxygen).

4.2.4. Additional secondary endpoints will analyze the immune response to herpesviruses by analyzing PD-1 expression by T lymphocytes and quantifying CMV- and EBV-antigen specific CD8⁺ T cell immune responses.

5. Background and Significance

5.1. Idiopathic pulmonary fibrosis - current status: IPF is a chronic progressive lung disease characterized by the insidious onset of interstitial infiltrates in the lung parenchyma associated with progressive dyspnea and impaired pulmonary function. Estimates for prevalence suggest that approximately 20 per 100,000 males and 13 per 100,000 females have the disease, and depending on the criteria used to define IPF, the disease may have a higher prevalence(1). The clinical definition of IPF requires exclusion of other known causes of interstitial lung disease, and its diagnosis requires characteristic changes on high-resolution computed tomography (HRCT), restriction on pulmonary function testing, impaired gas exchange, and absence of an alternative diagnosis on transbronchial biopsy or bronchoalveolar lavage (BAL)(11). Absolute confirmation of IPF by histologic diagnosis requires a surgical lung biopsy. The pathological equivalent of IPF is described as usual interstitial pneumonia (IPF/UIP). Of the Idiopathic Interstitial Pneumonias, IPF/UIP is the most common (70% of total) and most severe, so it is the form targeted in treatment trials(12). RCTs of interferon β and γ , bosentan, and sildenafil in IPF patients have been either negative or have shown inconsistent results, and there were no FDA approved therapies(13-17) until the recent approval of pirfenidone and nintedanib (18, 19). To date, clinical trials in IPF have been based on the premise that inhibition of inflammation or collagen deposition would be of benefit, or that treatment directed to the pulmonary vasculature would limit disease progression. In contrast, we suggest that therapy aimed at decreasing AEC injury and preserving alveolar epithelial function could be an effective approach.

5.2. Environmental factors in IPF: There are several lines of evidence that environmental factors are important in IPF. The lungs are continuously exposed to the environment and are at constant risk of microscopic and macroscopic environmental lung injury. A pathologic hallmark of IPF/UIP is spatial

and temporal heterogeneity of fibrotic remodeling. This feature is consistent with multiple episodes of microscopic lung injury by environmental stressors. Environmental risk factors linked to IPF in epidemiological studies include cigarette smoking(21), inhaled particulates(22), metal dust(23, 24), wood dust(23), and viral infections. Cigarette smoking has consistently been associated with increased risk for IPF with odds ratio from case-control studies ranging from 1.11-3.23. In addition to inhaled irritants, several viruses including adenovirus and herpesviruses have been associated with IPF(2, 3, 25, 26). A common feature of all these environmental factors is the ability to injure the alveolar epithelium. Interestingly, cigarette smoke(27, 28), inhaled particulates(29), and herpesviruses(30, 31) have all been shown to induce endoplasmic reticulum (ER) stress in lung epithelium, which we believe is an important underlying abnormality in IPF that predisposes to injury and limits recovery of the epithelial barrier.

5.3. Alveolar Epithelium in IPF: Our current concept for the pathogenesis of IPF is repeated injury of the alveolar epithelium followed by incomplete epithelial repair that results in an aberrant wound healing response, leading to pulmonary fibrosis. A variety of studies have emphasized the role of the alveolar epithelium in both clinical IPF and animal models of lung fibrosis. In lung biopsies from patients with IPF, epithelial abnormalities are common and include hyperplastic type II AECs and bronchiolar-like epithelial cells lining areas of honeycombing(32). The importance of AECs in IPF is highlighted by the identification of mutations in the epithelial-restricted genes, surfactant protein C (*SFTPC*) and *SFTPA2*, that are associated with Familial Interstitial Pneumonia (FIP), the familial form of IPF(33, 34). AECs engineered to express mutant forms of these genes result in protein products that are misfolded and accumulate in the ER, induce ER stress, and alter cell survival(35, 36). In 2008, we evaluated human lung tissues samples from FIP patients with a mutation in *SFTPC* (L188Q), FIP patients without *SFTPC* mutations, and sporadic IPF patients for expression of ER stress markers(4). These ER stress markers were prominently expressed in AECs lining areas of fibrosis in patients with *SFTPC* mutations as well as patients with lung fibrosis in the absence of *SFTPC* mutations. Subsequently, Korfei et al reported that AECs lining areas of fibrosis in IPF lung tissue sections not only had expression of ER stress markers, but these same cells also had activation of pro-apoptotic pathways(37). Recently, we developed a mouse model in which a mutant form of *SFTPC* is inducibly expressed in type II AECs(38). Such expression leads to ER stress in the type II AEC population, but these cells are able to maintain homeostasis in the setting of ER stress without the development of lung fibrosis. However, following low dose bleomycin, these mice develop excessive lung fibrosis. In a separate model, we induced ER stress in the lungs of wild type mice by intratracheal administration of tunicamycin(38). As with mutant *SFTPC* expression, ER stress alone did not cause lung fibrosis, but did predispose to greater bleomycin induced fibrosis. Taken together, these studies suggest that underlying ER stress leads to a vulnerable AEC population with predisposition to fibrosis after injury; however, a 'second hit' is necessary for development of lung fibrosis. We suggest that genetic predisposition and/or recurrent environmental stimuli render AECs vulnerable to a 'second hit' such as re-activation of herpesvirus that result in a pro-fibrotic cascade in the lung parenchyma.

5.4. Herpesvirus infection in IPF: Reports from several laboratories have demonstrated a striking association between herpesvirus infection in the lung and IPF. Increased titers of antibodies to cytomegalovirus (CMV) and Epstein Barr viral capsid antigen (EBV VCA) have been reported in patients with IPF and collagen vascular disease-related interstitial pneumonitis compared with controls(2). Using PCR for EBV DNA and immunohistochemistry (IHC) for EBV proteins, EBV VCA and LMP-1 (latent membrane protein 1) have been identified more frequently in biopsies from IPF patients than controls and only biopsies from IPF patients were positive by both IHC and PCR(26). Our group extended these investigations to identify all known herpesviruses by PCR for viral DNA. CMV, EBV, and Kaposi's sarcoma associated herpesvirus (KSHV, HHV-8) were present significantly more frequently in IPF lungs than controls, with 97% of IPF patients positive, whereas two other viruses reactivated by immunosuppression were not found(3). Furthermore, only IPF patients demonstrated co-infection with two or more herpesviruses. An important finding in these studies was that viral proteins were highly expressed in the abnormal airway epithelial cells lining distended airspaces in areas of honeycombing.

6. Protocol Design and Methods

6.1 **Study design:** We propose to conduct a single-center, prospective, randomized, placebo-controlled, double-blind pilot study of anti-herpesvirus therapy in patients with IPF. Patients with mild, moderate or severe IPF will be considered for study inclusion.

Randomization will be to pirfenidone plus placebo or pirfenidone plus valganciclovir. We prefer to have all subjects on pirfenidone as the standard of care for this study since the majority of patients elect to be treated with pirfenidone in our clinic. In addition, we anticipate valganciclovir will be better tolerated in combination with pirfenidone. We propose to enroll and randomize all eligible subjects with evidence of current or past EBV or CMV infection as determined by serologic testing for anti-EBV and CMV antibodies (total n=30) to treatment with pirfenidone plus valganciclovir (20 patients) or pirfenidone plus placebo (10 patients) for 12 weeks (**Fig. 1**). In order to maximize exposure to active treatment and assess for safety and tolerability, randomization will be 2:1 valganciclovir vs. placebo. The primary outcome will be safety and tolerability will be determined by type, frequency and duration of AE and SAEs. All study subjects will be offered bronchoscopy with BAL at study initiation and upon completion of treatment (12 weeks). Subjects will then be followed up at routine clinic visits at 6, 9 and 12 months for data collection.

[figure not shown]

Figure 1. Study flow chart.

6.2 **Rationale for Blinding and Placebo:**

6.1.1. A RCT is necessary given the clinical heterogeneity of IPF, and the inability to have two similar arms without randomization. A placebo arm will minimize bias since GI upset is a side effect of valganciclovir and standard treatment, pirfenidone. All subjects will be provided standard of care treatment to be applied equally across study groups as much as feasible and blinding will help avoid bias in the care provided.

6.1.2. Blinding is necessary to have optimal scientific validity, to make objective assessments of treatment effects, and to minimize dropout rates across study arms. In this study, there is particular concern that without blinding, subjects may opt to obtain off-label anti-viral therapy from non-study physicians if they become aware of the presence of herpesviruses in their lungs.

7. **Study population:** The study population will consist of male and female patients diagnosed with IPF, ages 21 and above, who are followed in the outpatient clinic setting.

7.1. **Inclusion criteria** will be:

- 7.1.1. age ≥ 21 and ≤ 80 years
- 7.1.2. ability to provided informed consent
- 7.1.3. diagnosis of probable or definite IPF according to ATS criteria(11)
- 7.1.4. tolerance of full-dose (2403 mg/day) pirfenidone
- 7.1.5. Positive serology for EBV or CMV

7.2. **Exclusion criteria** will be:

- 7.2.1. FVC $\leq 40\%$ predicted
- 7.2.2. DLCO $\leq 35\%$ predicted (Crapo)
- 7.2.3. FEV1/FVC < 0.7
- 7.2.4. Significant centrilobular emphysema ($> 40\%$ by HRCT)

- 7.2.5. Active tobacco use (cigarette or cigar smoking)
- 7.2.6. Resting SpO₂ on room air <89%
- 7.2.7. listed for lung transplantation defined as being assigned a lung allocation score
- 7.2.8. environmental exposure (occupational, environmental, drug, etc.) felt by the principal investigator (PI) to be the etiology of the interstitial disease
- 7.2.9. diagnosis of collagen-vascular conditions (according to the published American College of Rheumatology criteria)
- 7.2.10. history of unstable or deteriorating cardiac disease
- 7.2.11. acute coronary syndrome, coronary artery bypass, or angioplasty within 3 months of screening
- 7.2.12. uncontrolled arrhythmia
- 7.2.13. uncontrolled hypertension
- 7.2.14. known HIV or hepatitis C
- 7.2.15. known cirrhosis or chronic active hepatitis
- 7.2.16. active substance or alcohol abuse
- 7.2.17. pregnancy or lactation
- 7.2.18. Women of childbearing potential who are not using a medically approved means of contraception. Subjects will be considered of childbearing potential if they are not surgically sterile or have not been postmenopausal for at least 2 years [any subject who is postmenopausal for < 2 years will be required to have a follicle-stimulating hormone (FSH) level to assess her potential to become pregnant
- 7.2.19. clinically relevant lab abnormalities (obtained within 30 days before enrollment), including:
 - 7.2.19.1. creatinine > 2 x upper limit of normal (ULN)
 - 7.2.19.2. hematology outside of specified limits: white blood cells (WBCs) < 3,500/mm³; hematocrit < 25% or > 59%; platelets < 100,000/mm³
 - 7.2.19.3. total bilirubin > 2 x ULN
 - 7.2.19.4. Aspartate (AST) or alanine aminotransferases (ALT) (serum glutamic-oxaloacetic; transaminase [SGOT], or serum glutamic pyruvic transaminase [SGPT]) > 2.0 x ULN
 - 7.2.19.5. alkaline phosphatase > 3 x ULN
 - 7.2.19.6. albumin < 3.0 mg/dL at screening
- 7.2.20. known hypersensitivity to study medication
- 7.2.21. any condition that, in the judgment of the PI, might cause participation in this study to be detrimental to the subject or that the PI deems makes the subject a poor candidate
- 7.2.22. any therapy with immunosuppressants such as prednisone, azathioprine, or mycophenolate currently or anticipated to be needed during the study period (subjects on these drugs prior to the study will require a 30-day washout period before randomization)
- 7.2.23. participation in another IPF clinical treatment trial during the study period (if completing another IPF clinical treatment trial, then a 30-day washout period is required before randomization)
- 7.2.24. requirement for chronic suppressive therapy with valacyclovir for recurrent herpes virus infection
- 7.2.25. History of myelodysplasia, aplastic anemia, refractory anemia, or multiple myeloma.

8. Study Drug

- 8.1. *Dose justification of valganciclovir:* The standard dosing of valganciclovir for CMV disease when there is active pneumonitis with histopathologic changes such as intracellular inclusions, positive IHC, and acute inflammation is 900 mg twice daily(42). Typically, this occurs in solid organ or bone marrow transplant recipients, and is associated with viremia with viral loads in blood in the range of 10,000-100,000 viral genomes/ml(43). This dose is typically given for 21 days, and can be reduced 900 mg daily to further reduce low-grade viremia (200-2,000 copies/ml), and 900 mg/day can be given long term to prevent relapse or recurrent CMV disease(42). In IPF patients, CMV viral load in BAL is below 10,000 genomes/ml. Hence, the overall viral load is much lower in IPF patients compared to solid organ transplant recipients. Consequently, we believe a dose of 900 mg/day comparable to that used for chronic suppressive therapy in solid organ transplant recipients is most appropriate. A dose of 900

mg/day is generally well tolerated when administered for several months(42), and avoids the bone marrow suppression effects of long-term 900 mg twice daily dosing. Standard dosing of this regimen will be 900 mg once daily.

- 8.2. Justification of treating concomitant EBV and CMV with valganciclovir: Valganciclovir has activity against EBV and CMV. The 50% inhibitory concentration of valganciclovir against EBV is 1.5 mcg/ml(44), and the median area under the concentration versus time curve for 900 mg valganciclovir over 24 hrs (AUC₀₋₂₄) is 29 µg/ml with a peak concentration of 4.4 µg/ml(45). Hence the average concentration of valganciclovir is above the IC50 of EBV. We believe that monotherapy with valganciclovir should be effective and safe for subjects with CMV and EBV.
- 8.3. Protocol for dosage adjustment: In subjects who develop a treatment-emergent, nonserious adverse events (i.e. nausea), valganciclovir will be administered in divided doses (450 mg twice daily). In subjects who develop treatment emergent clinically significant laboratory abnormalities possibly related to the study drug, study drug will be held until lab abnormalities have resolved. Current and new medication review will be conducted to assess for alternative contributors to lab abnormalities. After the treatment-emergent laboratory abnormality resolves, subjects will then resume study drug with repeat laboratory monitoring within 1 week after resumption of treatment, or earlier if symptoms recur in an earlier time period. If the treatment emergent laboratory abnormality recurs, study drug will be reduced to 450mg QD with close monitoring. If symptoms or lab abnormalities occur with 450mg QD, the study drug will be terminated.

9. Study Feasibility and Timeline

All subjects will be enrolled through the Vanderbilt Interstitial Lung Disease (ILD) clinics have been top enrolling sites for several multi-center clinical trials in IPF, and given this proven track record, we are confident we will meet enrollment targets. We will place priority on enrollment in this VICTR support pilot trial over industry-sponsored trials. We currently evaluate >200 new IPF cases per year in our clinics. At the present time, approximately 125 IPF patients are being treated with pirfenidone in the Vanderbilt ILD clinic, and the majority of these patients should be eligible for this study. We expect to begin recruiting patients immediately upon approval of this study and complete enrollment within 9 months such that subjects will reach the primary study endpoint by the end of Year 1. Ongoing ascertainment of data collected during routine clinical follow-up of these study subjects will then be completed in Year 2.

10. Study Visits

